### *Tertiary outcomes*

Tertiary outcomes considered in this study are mainly self-reported patient outcomes. These are:

**Adherence to treatment.** This will be obtained from two self-reported variables recording how often, over the past month, the patient

- took his/her prescribed medication
- attended his/her planned appointment.

**Satisfaction with service.** This will be measured through the Client Satisfaction Questionnaire (CSQ-8) total score and Scale to Assess Therapeutic Relationships – Participant Version (STAR-P).

**Social and clinical outcomes.** These will be measured by the following instruments

- Brief Psychiatric Rating Scale (BPRS-24)
- Global Assessment of Functioning (GAF)
- Substance misuse history (CAGE)
- Health Related Quality of Life (EQ-5D)
- Insight and Treatment Attitudes Questionnaire (ITAQ)
- Drug Attitude Inventory (DAI-10)
- Psychiatry Autonomy Preference Index (API).

**Service usage.** This will be measured by the Client Service Receipt Inventory (CSRI).

**Patient rated experiences of pressure.** This will be measured by

- Mac Arthur Admission Experience Survey (AES)
- Index of fairness
- Index of effectiveness
- Experience of specific types of leverage questions.
- Types of pressure.

#### *Safety outcomes*

Safety outcomes include those self-reported items under Section 4 (Crime) of the CRF. These data, collected at 180 and 365 days, record whether the patient, in the previous six months,

- has been the victim of a non-violent crime;
- has been the victim of violent crime;
- has been self-harming;
- have harmed others

and if so how many times. Additional safety outcomes will include death and cause of death.

### **3. Study methods**

#### **Overall study design and plan**

The OCTET study was a randomised, parallel arm, non-blinded study of the effect on hospital readmissions for psychiatric treatment of discharge on CTO versus discharge on section 17 leave. The target for randomisation was 330 patients. The first randomisation took place on 10 November 2008 and the last on 22 February 2011.

#### **Target population**

##### *Inclusion criteria*

Patients were eligible if they were:

- Aged 18-65 years (in line with local administrative procedures for adult mental health services);
- Diagnosed with psychosis;
- Currently admitted under section 3 or section 37 (without restrictions) of the MHA;
- Not currently subject to any other legal restrictions;
- Judged by their clinicians (RC and AMHP) to need ongoing community treatment, but, having considered the relevant legal standards and clinical indicators, clinicians are genuinely uncertain as to which treatment mechanism would be appropriate;
- Able to consent to take part in research and give written and informed consent;
- Not having participated in the study (i.e. people with multiple admissions throughout the recruitment period should only participate in the study once).

##### *Exclusion criteria*

Patients were not eligible if they were:

- Unable to give informed consent (e.g. advanced dementia or mental disorder too severe to give informed consent);
- Subject to incompatible legal restrictions on treatment;
- Considered by their clinicians to be clear candidates for either a CTO or leave;
- Considered to be clear candidates for immediate discharge to voluntary treatment.

## **Method of treatment assignment and randomisation**

Randomisation was a stratified block design, with a 1:1 allocation ratio, and sequence assignment was unknown to all active members of the trial team until recruitment and data collection were completed. Eligible participants have an equal probability of assignment to each arm of the trial and the allocation ratio is 1:1. Participants are randomised individually to either CTO or Section 17 by an independent researcher using block randomisation with stratification factors for gender (male/female), schizophrenic status (yes/no), and duration of illness (< 2yrs, ≥ 2yrs). The randomisation code was developed using a computer random number generator to select random permuted blocks. The block lengths were 2, 4, and 6 varied randomly.

## **Treatment masking**

An independent statistician enclosed the treatment assignments in sequentially numbered, opaque, sealed envelopes which were stored by a researcher independent to the trial team. The details of the sequence remained unknown to all members of the trial team until recruitment and data collection were completed. The sealed envelope was labelled with the stratum number, gender, schizophrenic status, duration of illness and an envelope number. A matching label inside, also numbered, specified the intervention arm. Randomisation took place after consent was obtained and the baseline interview was performed. The envelope was opened following the interview by the independent researcher and communicated to the recruiting researcher by telephone. That researcher then informed the treating Responsible Clinician. The participant's trial identification number and date of randomisation were recorded on the appropriate envelope before it was opened.

## **Sample size determination**

Of the two previous RCTs on CTO, the study by Swartz and colleagues (1999) is considered the most rigorous. They reported a difference of 16% in the proportion readmitted to a psychiatric hospital within 12 months in patients under outpatient commitment compared to control. The sample size of 288 patients was determined as sufficient to detect a similar difference with a significance level of 5% and power of 80%, assuming rates of readmission were comparable in the control group. With this

number of patients, the following differences would also be detected as statistically significant, at the 5% level with 80% power:

- A 14-day difference in the mean number of days spent in hospital over 12 months;
- A difference of 0.43 in the mean number of readmissions over 12 months.

#### **4. *Data collection***

All primary outcome data were collected from medical records. Client Service Receipt Inventory was initiated from interview with patients but confirmed from case note examination. Notes from other hospitals and from the criminal justice system will be pursued when applicable.

A range of the secondary measures rely on patient interviews which are administered by the research assistants by reading out the questions contained in booklets specially designed for the RCT and recording the patient's reply. These booklets contain detailed assessment of demographics, clinical history, prior MHA use and criminal justice system contacts. They also record the assessment date, patient ID, interviewer ID, and time point. Current status will be assessed using the following well validated and widely used structured questionnaires:

- Mac Arthur Admission Experience Survey (AES)
- Index of fairness
- Index of effectiveness
- Psychiatry Autonomy Preference Index (API)
- Insight and Treatment Attitudes Questionnaire (ITAQ)
- Scale To Assess Therapeutic Relationships -Participant Version (STAR-P)
- Client Satisfaction Questionnaire (CSQ-8)
- Health Related Quality of Life (EQ-5D)
- Client Service Receipt Inventory (CSRI)
- Drug Attitude Inventory (DAI-10)
- Brief Psychiatric Rating Scale (BPRS-24)
- Global Assessment of Functioning (GAF)
- Substance Misuse History (CAGE).

The following non-validated instruments were also recorded:

- Experience of specific types of leverage;
- Patient Capabilities Questionnaire (PCQ), Quality of Life, which was applied in order to investigate its validity within the health economy analysis (not within the scope of this SAP);
- In addition, new items recording ‘Types of pressure’ in relation to experience of Leverage were included;
- A very small response rate is expected in the following validated questionnaire: Scale to Assess Therapeutic Relationships – Clinicians Version (STAR-C). It will be excluded from the analysis;
- The carer questionnaires will also be excluded from analysis as the patients in general did not have carers, and among those who had there was a low response rate ending up with only 30 questionnaires completed.

### **Timing of data collection**

Recruitment took place from 10 November 2008 to 22 February 2011. Potential participants were identified, informed of the trial and asked for consent prior to randomisation. The follow-up data were planned to be collected at six months after randomisation and at 12 months after randomisation.

### **Database**

#### *Description*

Data will be recorded in the CRFs by hand and double entered in SPSS.

#### *Data quality*

Double-entered data will be compared against each other and discrepancies will be discussed and corrected by the research assistants, supervised by [name].

#### *Database freeze*

[name], the statistician responsible for the analysis will conduct additional data quality evaluations. These include range checks, logical and consistency checks which may not be picked up by checks at the individual patient level by the research staff that

collected and entered the data. In the case of variables that are function of other variables (e.g. length of a particular hospitalisation), these will be checked by automatic calculation of its values, except for total scoring of the individual instruments which will be performed automatically by [name] using a validated code. The final cleaned data will be frozen before analysis starts.

## **5. General issues for statistical analysis**

### **Blinding of the statistical analysis**

The consultant statistician (MV) will remain blind to the treatment allocation until data are locked and final data analysis is to be conducted. The analysis statistician ([name]) carried out the two interim analyses but has remained blinded to the data collected since March 2011.

### **Analysis populations**

#### *Intent-to-treat population*

The Intention-to-treat population will include all randomised patients. Data from crossovers, drop-outs, or patients that never undertook the intervention assigned will be analysed according to their randomised group. Only one single withdrawal occurred during the trial. All available data from this patient will be included in analyses. There will be no per-protocol population as the trial was designed in a pragmatic way in which it was necessary that treating clinicians could change the legal status of the participant after their enrolment in the trial, if this was clinically appropriate in the opinion of the clinician at the time.

### **Major protocol violations**

Potential protocol violations:

- Discharge on the wrong arm (no matter when patients leave hospital);
- Patient withdrawn;
- Patient not eligible. Possible reasons:
  - Patient not eligible for CTO
  - Patient already on CTO
  - Patient not fulfilling inclusion/exclusion criteria.

Identified protocol violations:

- One patients self withdrew – Withdrew before T1 interview was completed;
- One patient had been on Section 17 for too long – T1 RCF is still available;
- One patient was already on a CTO – T1 RCF is still available.

### **Methods for handling missing data**

Given that the analysis is planned as an intention-to-treat analysis, data from all randomised patients will be included. Tertiary self-reported outcomes are likely to have missing values. For analysis involving these variables, missing data will be handled by multiple imputations using the *ice* stata command to generate a suitable number of imputed data sets and then using the *mim* stata command to automatically analyse each dataset and pool the results. The number of imputations will be chosen as follows:

- 1) The proportion of observed data will be calculated;
- 2) Assuming a tolerance for preventable power falloff <1%, a number of imputations  $m_I$  will be selected using Table 5 of Graham and colleagues' paper;
- 3) The proportion of information available will then be estimated using  $m_I$ ;
- 4) Table 5 will be used once again to obtain the final number of imputations  $m$  needed for the analysis.

The imputation model will potentially include all predictors of missing values (identified by fitting a logistic regression to each baseline variable on an indicator of missingness, for each variable with missing values), the primary, secondary and tertiary outcomes, and the stratification factors.

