### **Method for handling randomisation, stratification or minimisation factors**

Stratification variables (gender (male/female), schizophrenic status (yes/no), and duration of illness (< 2yrs, ≥ 2yrs)) will be adjusted for in the main analyses.

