### **Comparison of losses to follow-up**

As the main outcomes relate to hospital admissions data obtained from medical records, it is not expected that there will be any missing data for these outcomes. Participant self-reported outcomes derived from interviews and questionnaires are expected to contain substantial missing data.

The baseline characteristics of patients with and without data will be tabulated by treatment group and overall at each follow-up point for participant self-reported outcomes.

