### **Primary analysis**

The primary outcome, psychiatric hospitalisation in the 12 month follow-up period, will be analysed using log-binomial regression adjusted for stratification factors (gender (male/female), schizophrenic status (yes/no), and duration of illness (< 2yrs,  $\geq$  2yrs)). Results will be presented as the relative risk of readmission under CTO compared to Section 17, with appropriate 95% confidence interval and 2-sided p-values.

If log-binomial modelling is not possible due to model instability then other alternatives will be explored such as Poisson regression with robust error variances, a method which has the advantage of presenting results as relative risks; or logistic regression with associated odds ratios.

The primary analysis will be conducted on the ITT population. There will be no adjustment for missing data as it is not expected that there will be any.

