### **Tertiary analysis**

Tertiary analyses will be conducted using the ITT population once again. Where patient self-reported outcomes with missing data are analysed, these data will be imputed using multiple imputations (see Section 0).

For categorical outcomes such as self-reported adherence to treatment, substance misuse (CAGE), experience of specific types of leverage, and types of pressure chi-squared tests will be performed and no adjustments for stratification factors will be possible.

For continuous or pseudo-continuous outcomes (satisfaction with service (CSQ-8 and STAR-P), social and clinical outcomes (BPRS-24, GAF, EQ-5D, ITAQ, DAI-10, and API), service usage (CSRI), AES subscales, Index of fairness, and Index of effectiveness) linear regression models will be used.

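### The SAP's list of imputation-model variables does not include randomised arm, so any true between-arm difference in the imputed tertiary outcomes would be attenuated if the list is followed as written.

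*SAP*

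**What the plan says.** For self-reported tertiary outcomes, section 5 (Methods for handling missing data) states that "missing data will be handled by multiple imputations using the *ice* stata command", with pooling by a companion command. The variables are set out in one sentence: "The imputation model will potentially include all predictors of missing values" (these being "identified by fitting a logistic regression to each baseline variable on an indicator of missingness"), then "the primary, secondary and tertiary outcomes, and the stratification factors".

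Section 6 (Comparison of losses to follow-up) shows that the imputation will matter: "Participant self-reported outcomes derived from interviews and questionnaires are expected to contain substantial missing data". Section 10 (Tertiary analysis) applies it: "Where patient self-reported outcomes with missing data are analysed, these data will be imputed using multiple imputations". That section adds no variables to the imputation model.

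The primary analysis in section 8 is not imputed: "There will be no adjustment for missing data as it is not expected that there will be any". Section 9 takes the same position for the secondary outcomes. The repeated-measures sensitivity analysis in section 10 does without multiple imputation and names treatment, and its interaction with time, as fixed effects.

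**The concern.** The tertiary analyses compare the two arms. A missing score imputed from a model without arm is drawn as if the patient's allocation were irrelevant, except where another variable in the model happens to reflect it. The imputed scores in the two arms then resemble each other more than the true scores would, and the pooled difference moves towards zero.

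What is at stake is the main analysis of the tertiary outcomes, including satisfaction, symptoms, functioning, quality of life, insight and attitudes to medication. The secondary objective in section 2 concerns treatment adherence and social stability. Adherence and the social and clinical measures appear in the SAP only as tertiary outcomes, so a stated objective depends on these comparisons.

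**Working it through.** **1. Can arm enter by any listed route?**

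- Predictors of missingness: the screen covers baseline variables only, so arm does not enter here.
- Outcomes: arm is not an outcome. It can be reflected indirectly (step 3).
- Stratification factors: section 5 defines them in the sentence "Stratification variables (gender (male/female), schizophrenic status (yes/no), and duration of illness (< 2yrs, ≥ 2yrs)) will be adjusted for in the main analyses". Arm is not among them, and stratified 1:1 randomisation balances arm within them, so they carry no information on it.
- Imputation by arm: not stated anywhere.

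**2. Size if nothing in the model carries arm**

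The SAP gives no figure for the imputation, so there is none to reproduce. Let D be the true difference and f the missing fraction, equal in both arms. Observed scores differ by D and imputed scores by about 0, so

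expected estimate = D × (1 − f).

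This was checked by simulation.

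- From the SAP (section 3): 330 patients, the randomisation target, allocated 1:1.
- Assumed: a continuous score with D = 0.4 within-arm SD, a baseline covariate correlated 0.4 with the score and included in the imputation model, and data missing completely at random.
- Method: 20 imputations by Bayesian normal regression, linear regression on arm and three binary factors, Rubin's rules, 400 runs per setting.

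| Missing (assumed) | 1 − f | Simulated estimate ÷ D, no arm | Simulated, arm included |
|---|---|---|---|
| 10% | 0.90 | 0.91 | 1.00 |
| 20% | 0.80 | 0.78 | 0.98 |
| 30% | 0.70 | 0.70–0.72 | 1.00–1.03 |
| 40% | 0.60 | 0.59–0.60 | 0.99–1.01 |
| 50% | 0.50 | 0.50 | 0.98 |

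At 40% missing, power for this assumed effect is 0.42–0.44 without arm and 0.78–0.83 with it.

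**3. Size if a listed outcome is a partial proxy for arm**

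Time under legal compulsion is a secondary outcome, so it is on the list, and it counts time on a CTO. Suppose a standardised proxy has correlation r with arm and is related to the score only through arm. With arm coded ±1, the slope of score on proxy is rD/2 and the proxy means differ by 2r, so imputed scores differ by r²D. Then

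expected estimate = D × [(1 − f) + f × r²].

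At f = 0.40:

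| Assumed r | Formula | Simulated | Effect lost (simulated) | Power |
|---|---|---|---|---|
| 0.3 | 0.60 + 0.40 × 0.09 = 0.636 | 0.633 | 37% | 0.48 |
| 0.6 | 0.60 + 0.40 × 0.36 = 0.744 | 0.739 | 26% | 0.62 |
| 0.8 | 0.60 + 0.40 × 0.64 = 0.856 | 0.871 | 13% | 0.74 |

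A proxy reduces the loss but does not remove it.

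**4. No true difference**

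With D = 0 both formulas give 0, so there is no bias. The test becomes conservative because Rubin's variance is too large for an estimate shrunk in this way. At 40% missing (600 runs) a nominal 5% test rejected in 0.7% of runs without arm, 1.5% with a proxy at r = 0.6, and 5.8% with arm included.

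**The case against.** The strongest reply is that the list is provisional. It says what the model may include and is not stated to be exhaustive, and an experienced analyst would probably add arm unprompted. This stands in part: the fault is an omission, and a reader who infers that the plan deliberately excludes arm goes further than the text. But section 1.2 says the document sets rules to be followed as closely as possible. Followed closely, this list gives the attenuated result. Read loosely, it leaves an essential term to be settled at analysis.

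Second, the listed outcomes carry some of the arm effect. That is correct, so a reader should not infer that imputed scores would hold almost none of it; that is the limiting case in step 2. Nor does the SAP support assuming that most of it is recovered. Time under legal compulsion also counts section 17 time, so both arms accrue it, and section 5 (Intent-to-treat population) allows clinicians to change legal status after enrolment. Its correlation with arm cannot be read from the document.

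Third, a reader might conclude that a null tertiary result would be uninterpretable. That is too strong. For endpoints measured at several time points, the mixed-model sensitivity analysis includes treatment and does not share the fault, so attenuation could show as disagreement between the two analyses. It remains a sensitivity analysis, however, and the imputed comparison would still be the main result.

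Finally, the sentence on screening appears to reverse response and predictor. A reader might take this as a second methodological error. The missingness indicator is the evident intended response, so it is only loose phrasing.

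**Conclusion.** The point holds as an omission that should be fixed. If the variable list is followed as written, a true between-arm difference in an imputed tertiary outcome is attenuated by up to the missing fraction, and by less where listed outcomes partly stand in for arm. The direction of the attenuation follows from the structure of the model. Its size in this trial is unknown, because the SAP says only that missing data will be substantial and gives no effect size or correlations. The figures in the working illustrate a range and do not estimate this trial's loss. They also rest on a continuous score and data missing completely at random.

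The scope is the imputed tertiary outcomes only. The trial's primary conclusion and the secondary readmission and compulsion results do not depend on the imputation, and nothing here casts doubt on them.

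**What to change.** In section 5 (Methods for handling missing data), state that the imputation model always includes randomised arm, or that imputation is carried out separately within each arm. In the same sentence, state that each instrument's own baseline score is included where it was collected, whether or not it predicts missingness, since it will often be informative about the follow-up score.

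The cost is one or two sentences in the SAP and extra terms (or a by-arm run) in the imputation command. No new data are needed, and the primary and secondary analyses do not change.

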### **Method for handling centre effect**

Subgroup analyses comparing London versus other sites and Metropolitan versus non-metropolitan sites will be performed.

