### **Other analysis supporting the primary (including sensitivity analyses)**

A sensitivity analysis will be conducted for the primary outcome which is unadjusted for any stratification factors.

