### **Secondary analysis**

Secondary analyses will be conducted using the ITT population. No adjustment for missing data will be performed when analysing these outcomes as no missing data is expected for them.

Secondary outcomes will be analysed in the same way as primary outcomes using multiple regression models with adjustment for stratification factors. The type of regression model will depend on the data distribution. All model assumptions will be assessed.

Number of readmissions and number of nights in psychiatric hospitalization are count outcomes and will be analysed using Poisson or negative-binomial regression models depending on data dispersion. Results will be presented as incident-density ratios, which are interpreted in the same way as relative risks.

The number of nights to first readmission from INDEX to 365 days, and time under compulsion, are time to event outcomes and analyses will be performed using proportional hazards regression, with results presented as hazard ratios with 95% confidence intervals. Kaplan Meier plots will also be presented and the median time to readmission calculated with 95% confidence intervals.

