### **Other analysis supporting the tertiary analysis (including sensitivity analyses)**

A repeated measures sensitivity analysis will be conducted for endpoints measured at multiple time points using multivariable mixed-effects regression models. All available data from all participants will be included with missing values intrinsically imputed within the model rather than requiring multiple imputations. Treatment, stratification factors and time point (time since randomisation) will be entered into the model as fixed effects and the model will contain a patient specific random intercept. An interaction between time point and treatment group will be fitted as a fixed effect to allow estimation of treatment effect at each time point. We will also assess whether time should be included in the model as a random slope and different covariance structures will be explored to determine which model best fits the data.

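### The stated method for handling centre effect is two regional subgroup tests, so no planned treatment estimate allows for regional differences in readmission level; the cost is modest precision, not bias

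*SAP*

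**What the plan says.** SAP section 5, 'Method for handling centre effect', is a single sentence: "Subgroup analyses comparing London versus other sites and Metropolitan versus non-metropolitan sites will be performed". Section 12 defines a subgroup analysis of the primary endpoint as the primary model plus a treatment-by-subgroup interaction, and names the interaction p-value as the result of interest.

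The other places where site or region could enter do not include it:

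- Randomisation (section 3): "block randomisation with stratification factors for gender (male/female), schizophrenic status (yes/no), and duration of illness".
- Handling of stratification factors (section 5): these three variables "will be adjusted for in the main analyses".
- Primary model (section 8): the outcome "will be analysed using log-binomial regression adjusted for stratification factors".
- Supporting primary analysis (section 8): "A sensitivity analysis will be conducted for the primary outcome which is unadjusted for any stratification factors".
- Secondary models (section 9): analysed "using multiple regression models with adjustment for stratification factors".
- Repeated-measures model (section 10): "Treatment, stratification factors and time point (time since randomisation) will be entered into the model as fixed effects", with a patient random intercept.
- Further sensitivity analyses (section 5, time-varying interventions): these adjust for number of recalls and for delayed CTO start.

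The list under 'Planned sub-groups' contains neither London nor metropolitan status. Section 1.3 justifies the move to adjusted regression models by their greater precision.

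**The concern.** A section on handling centre effect should say how differences between centres are dealt with when the treatment effect is estimated. An interaction test answers another question, namely whether CTOs work differently in London or in metropolitan areas. If readmission is simply more common in one region in both arms, the interaction can be nil while region still adds noise to the comparison.

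Site was not a stratum, so regional balance between the arms is left to chance, and no planned model corrects for whatever imbalance arises. At stake are the width of the confidence interval and the reader's ability to see whether the CTO estimate is robust to regional mix. The plan argues for adjustment on grounds of precision and must classify every patient by region anyway, yet it does not use that variable in estimating the effect.

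**Working it through.** **Plan's own figures.** The SAP gives no number of sites, regional split or regional readmission rate, so it has no centre-effect figure to reproduce. Its sample size of 288 contains no site term. It is reached at an assumed control rate of about 46% or 70%, but the SAP does not state that rate, and the figure does not bear on this point.

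**Inputs.** From the SAP: 330 patients targeted (section 3, overall design), 1:1 individual allocation, and a 16-point design difference. Assumed: half the patients in London, 40% overall readmission risk, and a London-versus-other gap of 10, 20 or 30 points. The arithmetic is on the risk-difference scale and takes no treatment effect, so it indicates order of size only for the relative risk that the plan reports.

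**Chance imbalance.**
- SD of the arm difference in London share = sqrt(0.25 × 4 / 330) = 0.055.
- 95% range = ±1.96 × 0.055 = ±10.8 points.
- Resulting movement in the risk difference at a 20-point gap = 0.108 × 0.20 = ±2.2 points.

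**Total sampling error.**
- 95% half-width = 1.96 × sqrt(0.24 × 4 / 330) = 10.6 points.
- Share of variance due to region at a 20-point gap = (2.2 / 10.6)², about 4%.

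The ±2.2 points is therefore a component of the 10.6 points. It is the same quantity as the variance gain below, on another scale.

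**Variance removed by a region term**, as gap² × 0.25 / (0.40 × 0.60), next to 6,000 simulated trials of 330:

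| Gap | Formula | Simulated |
|---|---|---|
| 10 points | 0.01 × 0.25 / 0.24 = 1.0% | 0.7% |
| 20 points | 0.04 × 0.25 / 0.24 = 4.2% | 4.7% |
| 30 points | 0.09 × 0.25 / 0.24 = 9.4% | 9.1% |

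At a 20-point gap the half-width falls from 10.57 to 10.57 × sqrt(1 − 0.042) = 10.35 points, a gain of about 0.2 points.

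**Validity without adjustment.** A separate simulation used 288 patients, assumed risks of 48% and 32%, 8 or 30 sites, between-site SD 0 to 1.0 on the logit scale, and 3,000 runs per setting. It compared the unadjusted risk difference with a linear model containing site fixed effects.

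- Under no treatment effect, the unadjusted estimate averaged within 0.13 points of zero in every setting.
- Unadjusted type I error ran from 4.9% to 6.0% (simulation error about sqrt(0.05 × 0.95 / 3000) = 0.4 points), with no consistent rise as sites became more different.
- With 8 sites, site adjustment changed power from 80.5% to 80.3% (SD 0), from 79.8% to 81.5% (SD 0.6) and from 80.8% to 83.6% (SD 1.0).
- With 30 sites, it lowered power from 80.6% to 75.8% (SD 0) and was about neutral at SD 1.0 (79.5% to 80.4%).

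Many site fixed effects can therefore cost more than they gain. A coarse region term does not carry that cost.

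**The case against.** The strongest reply is that the main analysis is valid as written. Patients are randomised individually and the models adjust for exactly the factors that restricted the randomisation. Adjustment for site is most clearly required when site is a stratum, and here it is not. This stands: omitting region causes neither bias on average nor inflated type I error.

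The size also depends on inputs the SAP does not give. At a 10-point gap the gain is about 1%, and nothing in the document shows that readmission differs strongly by site. This stands too, and is why the result is given as a range.

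Three stronger readings might be inferred, and the document supports none of them:

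- That the ±2.2 points is an extra error to set against the 16-point design difference. It already lies inside the confidence interval.
- That the sponsor expects large regional differences. Planning a subgroup test shows only that region was thought worth examining; the subgroup list also holds marital status and country of birth.
- That region appears in no fitted model at all. A conventional interaction model would include its main effect. Those models are not, however, the source of the reported treatment effect.

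Finally, the analysis statistician ran two interim analyses that compared primary and secondary outcomes. Changing the primary model afterwards could be called post hoc. That is a fair reason to allow a sensitivity analysis instead. It does not justify leaving region out of every estimate.

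**Conclusion.** The point holds as a matter of precision and robustness. The section on centre effect prescribes a method that does not account for centre or regional differences in the reported treatment effect, and no other part of the SAP does so. The planned estimate remains unbiased on average with valid type I error.

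Under the assumptions shown, the loss is about 1% to 9% of the variance for regional gaps of 10 to 30 points. It would change with a different London share, overall risk or gap. The improvement is small but cheap, and it follows the plan's own argument for adjusted models. The missing entries in the subgroup list are a separate inconsistency that needs no assumptions.

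**What to change.** Before final unblinding:

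1. In 'Method for handling centre effect', define region from the two splits already named and state which sites count as metropolitan. If London counts as metropolitan, the splits give three levels.
2. Add region as a main-effect covariate next to the stratification factors in the primary model (section 8) and the secondary models (section 9). If the sponsor prefers not to change the primary model after the interim analyses, add at minimum a pre-specified region-adjusted sensitivity analysis of the primary outcome to section 8.
3. Keep the two regional interaction tests as exploratory and add them to 'Planned sub-groups'.

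The cost is SAP wording and one or two more parameters per model. Site must already be classified for the regional tests. The risk that the log-binomial model fails to converge rises slightly; section 8 already names Poisson regression with robust errors as an alternative.
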